4.1 SUPPORTIVE CARE

Patient should receive general concomitant and supportive care medications based on best medical practice.

The use of any natural/herbal products or other “folk remedies” should be discouraged.

Olaparib is an investigational drug for which no data on in vivo interactions are currently available. Based on in vitro data and clinical exposure data, olaparib is considered unlikely to cause clinically significant drug interactions through inhibition or induction of cytochrome P450 enzyme activity. In vitro data have, however, also shown that the principal enzyme responsible for the formation of the 3 main metabolites of olaparib is CYP3A4 and consequently, to ensure patient safety, the following potent inhibitors of CYP3A4 must not be used during this study for any patient receiving olaparib.

While this is not an exhaustive list, it covers the known potent inhibitors, which have most often previously been reported to be associated with clinically significant drug interactions:

- ketoconazole, itraconazole, ritonavir, idinavir, saquinavir, telithromycin, clarithromycin and nelfinavir

For patients taking any of the above, the required wash-out period prior to starting olaparib is one week.

In addition, to avoid potential reductions in exposure due to drug interactions and therefore a potential reduction in efficacy, the following CYP3A4 inducers should be avoided:

- Phenytoin, rifampicin, rifapentine, rifabutin, carbamazepine, phenobarbitone, nevirapine, modafinil and St John’s Wort (*Hypericum perforatum*)

For patients taking any of the above, the required wash-out periods prior to starting olaparib are:

- phenobarbitone 5 weeks, and for any of the others, 3 weeks.

4.1.1 Other Concomitant Medications

All medications (prescriptions or over-the-counter medications) continued at the start of the trial or started during the study or until 30 days from the end of the last protocol treatment and different from the study medication must be documented.

Anticoagulant Therapy: Subcutaneous heparin is permitted.

4.1.2 Palliative radiotherapy

Palliative radiotherapy may be used for the treatment of pain at the site of bony metastases that were present at baseline, provided the Investigator does not feel that these are indicative of clinical disease progression during the study period. Study treatment should be discontinued for a minimum of 3 days before the patient undergoes palliative radiation treatment. Study treatment should be restarted within 28 days from the scheduled date as long as any bone marrow toxicity has recovered.

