3.3.2 Dosing Delays/Dose Modifications and Management of Toxicities

- In the case of toxicity, appropriate medical treatment should be used (including anti-emetics, anti-diarrheals, etc.).
- Once a patient has a dose reduction for toxicity, the dose will not be increased.
- A maximum of 2 dose reductions is permitted
- If either agent is discontinued due to toxicity, the patient may continue on the other agent.
- Participants continuing to experience toxicity at the off treatment visit will be contacted for additional assessments until the toxicity has resolved or is deemed irreversible. Patients must remain on the study to have additional assessment.
- For AEs that are unrelated to the study drugs, study drug may be held for up to 21 days at the discretion of the PI.
- The associate investigator and/or PI will determine whether one or both drugs are responsible for an observed toxicity and will manage that toxicity as described below.

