3.3.2.1 Hematologic toxicities

Table 8. Dose Modification and Management of Hematologic Adverse Events

Observation	Action
On day 1 and 15 Absolute neutrophil count (ANC) \geq 1500/mcL AND Platelets \geq 75,000/mcL AND Hemoglobin \geq 8 g/dL	No interruption.
On day 1 and 15 ANC $<$ 1500/mcL OR Platelets $<$ 75,000/mcL OR Hemoglobin $<$ 8 g/dL	If any weekly evaluation demonstrates grade \geq 3 neutropenia or grade \geq 2 thrombocytopenia, a repeat hematology assessment will be obtained 2-4 days later. On first occurrence , hold the drug(s) causing the toxicity for up to 21 days until ANC \geq 1500/mcL, platelets \geq 75,000/mcL, and hemoglobin \geq 9 g/dL. The associate investigator and/or PI will determine whether one or both drugs are responsible for an observed toxicity and will initiate appropriate medical therapy and no change in dose upon re-initiation. On second occurrence , hold the drug(s) causing the toxicity for up to 21 days until ANC \geq 1500/mcL, platelets \geq 75,000/mcL, and hemoglobin \geq 9 g/dL. Initiate appropriate medical therapy. Treatment with olaparib or EP0057 may be restarted at one dose level (DL) lower. Patients whose counts have not recovered to ANC \geq 1500/mcL, platelets \geq 75,000/mcL, and hemoglobin \geq 9 g/dL after 21 days should be removed from the drug causing the toxicity.
At any time during cycle Grade 4 hematologic AE	On first occurrence , hold the drug(s) causing the toxicity for up to 21 days until ANC \geq 1500/mcL, platelets \geq 75,000/mcL, and hemoglobin \geq 9 g/dL. Initiate appropriate medical therapy. Treatment with olaparib or EP0057 may be restarted at one DL lower. On second occurrence , discontinue the drug(s) causing the toxicity. Follow patient until

Table 8. Dose Modification and Management of Hematologic Adverse Events

Observation	Action
	resolution/stabilization of toxicity. Patients whose counts have not recovered to ANC \geq 1500/mcL, platelets \geq 75,000/mcL, and hemoglobin \geq 9 g/dL after 21 days should be removed from the drug causing the toxicity. See section 3.3.2.1 for exceptions.
Toxicities requiring more than 2 dose reductions	Remove patient from the drug causing the toxicity.

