- Treatment may be delayed for a maximum of 21 days after holding the treatment for toxicities that develop and do not resolve as defined above (the following AE's are exempt from hold: lymphopenia, or leukopenia in the absence of grade 3 or higher neutropenia).
- Weekly blood counts will be obtained during the first cycle, and then at day 1 and 15 of subsequent cycles.
- Management of prolonged hematological toxicities while on study treatment
 - If a patient develops prolonged hematological toxicity such as:
 - \geq 2 week interruption/delay in study treatment due to CTC grade 3 or worse anemia and/or development of blood transfusion dependence
 - \geq 3 week interruption/delay in study treatment due to CTC grade 3 or worse neutropenia (ANC $<$ 1,000/mcL)
 - \geq 3 week interruption/delay in study treatment due to CTC grade 3 or worse thrombocytopenia (Platelets $<$ 50,000/mcL)
 - Weekly differential blood counts including reticulocytes (calculate reticulocyte index (RI), RI = reticulocyte count x hematocrit (Hct)/normal Hct; a value of 45 is usually used for normal Hct) and peripheral blood smear should be performed. If any blood parameters remain clinically abnormal after 4 weeks of dose interruption, the patient should be referred to hematologist for further investigations. Bone marrow analysis and/or blood cytogenetic analysis should be considered at this stage according to standard hematological practice.
 - Development of a confirmed myelodysplastic syndrome or other clonal blood disorder should be reported as an SAE. Study treatment should be discontinued if diagnosis of myelodysplastic syndrome is confirmed.

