3.3.5 Dose Modification for Surgical Procedures or Palliative Radiation

- Olaparib should be stopped 3 days before surgery and re-started after wound has healed following recovery.
- No stoppage of olaparib is required for any biopsy procedures.
- Olaparib should be discontinued for a minimum of 3 days before a patient undergoes therapeutic palliative radiation treatment.

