3.6.1 Criteria for Removal from Protocol Therapy

- Progressive disease
- Participant requests to be withdrawn from active therapy
- Unacceptable Toxicity as defined in Sections [3.1.1](#) and [3.3](#)
- Toxicity related dose delay lasting longer than 21 days in which case patient will be removed from the drug causing the toxicity.
- Investigator discretion
- Requirement for any of the prohibited study drugs as described in [Appendix B](#), Section [16.2](#) (Strong and moderate Inhibitors and Inducers of CYP3A)
- The subject becomes pregnant
- Active pneumonitis

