14.1.6 Dosage and Administration

See Sections 3.2 and 3.3 for the dose levels and administration of EP0057 to be evaluated in this study.

See Section 3.3.4 for management of any EP0057 infusion related/hypersensitivity reactions.

The second and subsequent dose of EP0057 may be delayed if related AEs have not resolved to grade 1 or better. If a dose of EP0057 is delayed, then the subsequent dose should be administered 2 weeks later to avoid significant carry-over of unconjugated plasma CPT from one dose to the next (see Section 3.3). However, the maximum delay for AEs to resolve is 21 days beyond which the patient will be taken off treatment.

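### The two palliative-radiotherapy rules differ on which drugs are stopped, and the 28-day restart is not reconciled with the 21-day limit on marrow-toxicity delays

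*Combined protocol and SAP*

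**What the plan says.** Section 3.3.5, on dose modification, gives this rule: "Olaparib should be discontinued for a minimum of 3 days before a patient undergoes therapeutic palliative radiation treatment". It does not mention EP0057 and sets no time limit for restarting.

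Section 4.1.2, on concomitant measures, uses the same interval for a wider object: "Study treatment should be discontinued for a minimum of 3 days before the patient undergoes palliative radiation treatment". It continues: "Study treatment should be restarted within 28 days from the scheduled date as long as any bone marrow toxicity has recovered". It defines neither the scheduled date nor recovery. Neither section refers to the other.

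The toxicity rules work with 21 days:

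- Table 8 in section 3.3.2.1 says that patients whose counts have not reached its thresholds (ANC 1500/mcL, platelets 75,000/mcL, hemoglobin 9 g/dL) "after 21 days should be removed from the drug causing the toxicity".
- The text below Table 8 says: "Treatment may be delayed for a maximum of 21 days after holding the treatment for toxicities".
- Section 3.6.1 lists as a ground for removal: "Toxicity related dose delay lasting longer than 21 days in which case patient will be removed from the drug causing the toxicity".
- Section 14.1.6, on delayed EP0057 doses, says that "the maximum delay for AEs to resolve is 21 days beyond which the patient will be taken off treatment".
- Section 3.3.2 says that, for adverse events unrelated to the study drugs, "study drug may be held for up to 21 days at the discretion of the PI". It also lets a patient who stops one agent for toxicity stay on the other.

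**The concern.** Section 4.1.2 permits palliative radiotherapy for painful bone metastases that were present at baseline, so these rules can come into use. Elsewhere the protocol treats the two drugs as separable: sections 3.3.2 and 3.3.3 let one be held or stopped while the other goes on. Naming one drug in section 3.3.5 and the whole regimen in section 4.1.2 therefore has practical meaning.

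The protocol's own background gives the difference weight. Section 1.2.5 reports that PARP inhibition makes cancer cells more sensitive to ionizing radiation. Section 1.2.6 describes EP0057 as releasing camptothecin in tumor over several days. On that account, which drugs are present at irradiation is a safety matter.

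The second difficulty is resumption. If counts are low after radiotherapy, the team finds a 28-day window in one section and a 21-day limit in several others, with no order of precedence. An action that follows one section may then be a deviation from another.

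**Working it through.** The plan states no figure on this point, so there is none to reproduce. The check sets the texts side by side and counts days.

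**1. What is stopped before radiation**

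| | Section 3.3.5 | Section 4.1.2 |
|---|---|---|
| Stopped | Olaparib | Study treatment |
| Minimum interval | 3 days | 3 days |
| EP0057 | Not mentioned | Included as part of study treatment |
| Restart | No limit given | Within 28 days of the scheduled date, if marrow has recovered |

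**2. Whether the difference can arise on the planned schedule**

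Inputs: EP0057 on days 1 and 15 of a 28-day cycle (section 3.1). The last olaparib doses are on the mornings of days 13 and 26, and olaparib resumes on day 17 and on day 3 of the next cycle (section 3.2.2 and the pill diary in Appendix C).

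- Radiation on day 16: olaparib has been off for 16 − 13 = 3 days, so section 3.3.5 is met with no schedule change. EP0057 was infused 16 − 15 = 1 day earlier, so the 3 days in section 4.1.2 are not met.
- Radiation on day 2 of the next cycle (day 30 counted from the previous day 1): olaparib has been off for 30 − 26 = 4 days, and EP0057 was infused 30 − 29 = 1 day earlier. The result is the same.

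The planned olaparib gaps surround the EP0057 infusions, so the two sections can give different answers on ordinary schedule days.

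**3. Restart against removal**

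Section 4.1.2 counts from the scheduled date. Section 3.3.2.1 counts from the hold for toxicity. Let *s* be the day on which the toxicity hold starts, counted from the scheduled date.

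- The 21-day limit expires on day *s* + 21.
- The radiotherapy restart window closes on day 28.
- The instructions on the causative drug oppose each other if counts recover after day *s* + 21 and by day 28. That is 28 − (*s* + 21) = 7 − *s* days.

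| Toxicity hold starts | Days of recovery in conflict | Length |
|---|---|---|
| 3 days before the scheduled date (*s* = −3) | 19 to 28 | 10 days |
| On the scheduled date (*s* = 0) | 22 to 28 | 7 days |
| 3 days after (*s* = 3) | 25 to 28 | 4 days |
| 7 or more days after (*s* ≥ 7) | None | 0 |

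Because the scheduled date is undefined, *s* = 0 is an assumption and the table shows the range.

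**4. Whether other text settles it**

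The 28-day period in section 3.1.1 is a phase I dose-limiting-toxicity criterion. The 4 weeks of interruption mentioned in section 3.3.2.1 trigger referral to a hematologist. Neither is a restart rule, and neither mentions radiotherapy. The exemptions from holding in section 3.3.2.1 cover lymphopenia, and leukopenia without grade 3 or higher neutropenia; radiotherapy is not among them.

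**The case against.** The strongest reply on the first part is that section 3.3.5 is silent on EP0057 and does not say to continue it. All its bullets concern olaparib, and stopping the whole regimen under section 4.1.2 also satisfies section 3.3.5. That stands: this is a difference of scope, and both rules can be obeyed at once. But someone who consults only the dose-modification section finds no instruction on EP0057 and no pointer to section 4.1.2.

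On the second part, section 4.1.2 makes marrow recovery a condition for restart and does not cancel the toxicity rules. Table 8 and section 3.6.1 act only on a drug that caused the toxicity. If low counts are put down to radiation alone, there is no causative study drug to remove; the 21-day hold for unrelated events in section 3.3.2 is discretionary and prescribes no removal. This also stands, and it confines the conflict to toxicity attributed to a study drug. It does not remove the conflict there, because nothing says that section 4.1.2 is subject to the 21-day limit.

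A reader might infer three stronger things that the documents do not support:

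- *That a patient is both restarted and removed from therapy altogether.* Removal under Table 8 is drug-specific, and section 3.3.2 lets the other agent continue. Only section 14.1.6, for EP0057 delays, is worded more broadly.
- *That sites would diverge.* Section 3.1 describes a single-center trial; the risk is that staff rely on different sections.
- *That the 16-week result depends on which rule is used.* Section 6.3.7 runs PFS from start of treatment to progression or death, and section 10.1 counts success as reaching 16 weeks without progression. Neither requires the patient still to be on the combination.

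**Conclusion.** The point holds as a minor inconsistency in wording, in two parts.

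First, sections 3.3.5 and 4.1.2 differ in scope on what is stopped before palliative radiation. Radiation on day 16 of the planned schedule shows the difference: it meets one section and breaches the other.

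Second, for marrow toxicity attributed to a study drug, the 28-day restart and the 21-day limits give opposite instructions on restarting that drug when counts recover after the 21-day limit but by day 28. It would be too strong to say that every recovery on days 22 to 28 is affected. That span assumes that both clocks start together; it lengthens if the toxicity hold starts earlier, shortens if it starts later, and disappears from 7 days on.

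The frequency cannot be estimated, because the documents do not give the number of patients expected to be irradiated. Sample size, alpha and power are unaffected. No view is taken on which clinical rule is right.

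**What to change.** The sponsor should:

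- reconcile sections 3.3.5 and 4.1.2 so that both name the same drug or drugs to be stopped before palliative radiation;
- reconcile the 28-day restart in section 4.1.2 with the 21-day limits in sections 3.3.2, 3.3.2.1 (including Table 8), 3.6.1 and 14.1.6, stating which governs when marrow toxicity accompanies a radiotherapy interruption;
- define the scheduled date and marrow recovery in section 4.1.2, and state the date from which each clock runs;
- cross-refer the sections to each other.

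The cost is a wording amendment. It adds no visits, procedures or patients.

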4.1.3 Administration of other anti-cancer agents

Patients must not receive any other concurrent anti-cancer therapy, including investigational agents, while on study treatment. Patients may continue the use of bisphosphonates for bone disease and corticosteroids for the symptomatic control of brain metastases provided the dose is stable before and during the study

4.1.4 Medications that may NOT be administered

- No other chemotherapy, immunotherapy, hormonal therapy or other novel agent is to be permitted while the patient is receiving study medication. For the mCRPC cohort, patients may receive hormonal therapy in the form of GnRH agonists/antagonists as per eligibility criteria above.

4.1.5 Overdose

There is currently no specific treatment in the event of overdose with olaparib and possible symptoms of overdose are not established.

Olaparib must only be used in accordance with the dosing recommendations in this protocol. Any dose or frequency of dosing that exceeds the dosing regimen specified in this protocol should be reported as an overdose.

Adverse reactions associated with overdose should be treated symptomatically and should be managed appropriately.

4.2 HIGHLY EFFECTIVE METHODS OF BIRTH CONTROL

The study drugs used in the study are regarded as having with medium/high fetal risk.

Individuals of childbearing potential and their partners, who are sexually active, must agree to the use of one highly effective form of contraception and their partner must use a condom [as listed below]. This should be started from the signing of the informed consent and continue throughout the period of taking study treatment and for at least 6 months after last dose of study drug(s), or they must totally/truly abstain from any form of sexual intercourse (see below).

Individuals who can father children must use a condom during treatment and for 3 months after the last dose of olaparib when having sexual intercourse with a pregnant woman or with a woman of childbearing potential. Their partners should also use a highly effective form of contraception if they are of childbearing potential (as listed below). Individuals who can father children should not donate sperm throughout the period of taking olaparib and for 3 months following the last dose of olaparib.

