- creatinine clearance	≥ 51 mL/min (calculated using the Cockcroft-Gault formula) for patients with creatinine levels above institutional normal.

2.1.2.10 Individuals who can father children and their partners must agree to use highly effective contraception (refer to section 4.2 for details) prior to study entry, for the duration of study participation and for 3 months following last dose of study drugs. Individuals who are of childbearing potential and sexually active must agree to the use of 1 highly effective form of contraception, and their partners, if they can father children, must use a condom, or they must totally/truly abstain from any form of sexual intercourse, throughout their participation in the study and for at least 6 months after last dose of study drugs. Individuals should not donate sperm throughout the period of taking olaparib and for 3 months following the last dose of olaparib. Individuals of childbearing potential (IOCBP) are defined as being physically capable of becoming pregnant unless unable to have children because of surgery or other medical reasons (effective tubal ligation, ovaries or the uterus removed, or are post-menopausal). Post-menopausal is defined as:

- Amenorrheic for 1 year (12 months in a row) or more following cessation of exogenous hormonal treatments,
- LH and FSH levels in the post-menopausal range for individuals under 50,
- radiation-induced oophorectomy with last menses >1 year ago,
- chemotherapy-induced menopause with >1 year interval since last menses,
- or surgical sterilization of participant (bilateral oophorectomy or hysterectomy) and/or partner.

2.1.3 Inclusion Criteria for Urothelial Carcinoma Expansion Cohort (accrual to the cohort ended with amendment version 08/17/2022)

2.1.3.1 Patients must have a histologically confirmed diagnosis of urothelial carcinoma of the bladder, urethra, ureter, or renal pelvis from a CLIA-certified laboratory, with measurable disease by RECIST (version 1.1) including lymphadenopathy and visceral metastatic disease

2.1.3.2 Adult patients ≥ 18 years of age.

2.1.3.3 Patient must have received at least one platinum based regimen of chemotherapy and/or an immune-checkpoint inhibitor if appropriate with progressive disease.

2.1.3.4 Prior antiangiogenic and radiation therapy are permitted (2-week washout from therapy is required).

2.1.3.5 Bisphosphonates and denosumab are permitted if on a stable dose for ≥ 4 weeks.

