4.2.1 Acceptable non-hormonal birth control methods

- Total/true abstinence: When the patient refrains from any form of sexual intercourse and this is in line with their usual and/or preferred lifestyle; this must continue for the total duration of the study treatment and for at least 6 months (for individuals able to bear children) or at least 3 months (for individuals able to father children) after the last dose of study treatment. Periodic abstinence (eg, calendar ovulation, symptothermal, post-ovulation methods, or declaration of abstinence solely for the duration of a trial) and withdrawal are not acceptable methods of contraception.
- Vasectomised sexual partner PLUS condom (with participant assurance that partner received post-vasectomy confirmation of azoospermia).
- Tubal occlusion PLUS condom.
- Intrauterine device (provided coils are copper-banded) PLUS condom.

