8.6.2 Paternal exposure

Patients should refrain from fathering a child or donating sperm during the study and for (3 months) after the last dose of EP0057 or olaparib.

Pregnancy of the patient's partner is not considered to be an AE. The outcome of all pregnancies occurring from the date of the first dose until (3 months) after the last dose should, if possible, be followed up and documented. Pregnant partners may be offered the opportunity to participate in an institutional pregnancy registry protocol (e.g., the NIH IRP pregnancy registry study) to provide data about the outcome of the pregnancy for safety reporting purposes.

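### Sections 2.1.2.10 and 4.2 time the sperm-donation ban, and 4.2 the post-treatment condom period, from the last olaparib dose only, although a man may continue on EP0057 alone

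*Combined protocol and SAP*

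**What the plan says.** Sperm donation is addressed in three places that matter for the open SCLC cohort.

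- Section 2.1.2.10 (Phase II SCLC inclusion criteria): "Individuals should not donate sperm throughout the period of taking olaparib and for 3 months following the last dose of olaparib".
- Section 4.2 sets the same olaparib-only period, under which men "should not donate sperm throughout the period of taking olaparib and for 3 months following the last dose of olaparib".
- Section 8.6.2, on paternal exposure, asks them to "refrain from fathering a child or donating sperm during the study and for (3 months) after the last dose of EP0057 or olaparib".

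On condoms, the 4.2 rule for men is that they "must use a condom during treatment and for 3 months after the last dose of olaparib when having sexual intercourse with a pregnant woman", and it extends to partners who could conceive.

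Other reproductive rules count both drugs. The contraception clause for men and their partners in 2.1.2.10 applies "for the duration of study participation and for 3 months following last dose of study drugs" and refers to 4.2 for details. The abstinence rule for men in 4.2.1 counts from the end of study treatment. The 6-month rule for individuals of childbearing potential in 4.2 counts from the study drug or drugs. Section 4.2 itself opens: "The study drugs used in the study are regarded as having with medium/high fetal risk".

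Section 3.3.2 allows a patient to stay on one agent when the other is stopped for toxicity. Sections 3.3.3 and 3.6.1 likewise hold or remove only the drug held responsible.

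**The concern.** The olaparib date is a safe reference only when olaparib is the last drug taken. That is so on the normal schedule, where each EP0057 infusion is followed by olaparib, and also when EP0057 is the drug stopped first. It fails in one permitted course: olaparib is stopped for toxicity and EP0057 goes on. The donation and post-treatment condom clocks then start while the man is still receiving a cytotoxic drug that the protocol treats as a fetal risk.

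No reason is given for leaving EP0057 out, and the neighbouring rules include it, so the wording looks like an oversight. What is at stake is the end date that staff give a man when they counsel him. Section 2.1.2.10 sends them to 4.2 for contraception details; the longer donation period sits in a pregnancy-reporting section, where they are less likely to look.

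**Working it through.** The plan states no figure here to reproduce. The check compares clauses and then works through the dosing calendar.

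**Comparison of end dates**

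| Rule for men | Section | Post-treatment clock starts at last dose of |
|---|---|---|
| Sperm donation | 2.1.2.10, 4.2 | olaparib |
| Sperm donation | 8.6.2 | EP0057 or olaparib |
| Condom, including with a pregnant partner | 4.2 | olaparib |
| Contraception with partner | 2.1.2.10 | study drugs |
| Abstinence | 4.2.1 | study treatment |

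**Inputs.** Cycles last 28 days, with EP0057 on days 1 and 15 (3.1) and olaparib on days 3–13 and 17–26 (3.2.2). Assumptions: 3 months is 91 days; olaparib ends on day 26 of a cycle; n full cycles of EP0057 alone follow. The documents do not give n.

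**Gap between last doses.** Counting from the start of the last olaparib cycle, the last EP0057 dose falls on day 28n + 15. The gap is (28n + 15) − 26 = 28n − 11 days. This is how much earlier the donation ban ends under 2.1.2.10 and 4.2 than under 8.6.2.

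**Condom period left after the last EP0057 dose**, reading the 4.2 sentence alone: max(0, 91 − gap).

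| EP0057-only cycles (n) | Gap (days) | Condom days left | Shortfall from 91 |
|---|---|---|---|
| 1 | 28 − 11 = 17 | 74 | 17 |
| 2 | 56 − 11 = 45 | 46 | 45 |
| 3 | 84 − 11 = 73 | 18 | 73 |
| 4 | 112 − 11 = 101 | 0 | 91 |

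The post-treatment condom period disappears only in the fourth EP0057-only cycle. If olaparib stopped at the end of cycle 1, that is cycle 5, weeks 17–20.

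**Longer example.** Olaparib ends on day 26 of cycle 1 and EP0057 alone continues to day 15 of cycle 6, which is day 5 × 28 + 15 = 155. Under 4.2 the donation ban ends on day 26 + 91 = 117, which is 155 − 117 = 38 days before the last infusion. Under 8.6.2 it ends on day 155 + 91 = 246. The difference is 246 − 117 = 129 days, matching 28 × 5 − 11.

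**Trivial case.** If all treatment ends just after an EP0057 infusion and before olaparib restarts, the gap is 15 − 13 = 2 days or 29 − 26 = 3 days.

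**Who is affected.** Partners who could conceive are already covered by the 2.1.2.10 contraception clause, which counts both drugs. Every method in 4.2.1 and 4.2.2 other than abstinence also requires a condom, for example "Tubal occlusion PLUS condom". That leaves the already pregnant partner, whom 4.2 names explicitly.

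**The case against.** The strongest reply is that the protocol, read as a whole, already protects everyone. Three parts of it carry weight.

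**Donation.** A reader might infer that a man on EP0057 alone is free to donate once 3 months have passed since olaparib. The documents do not support that. Section 8.6.2 bars donation during the study and for the longer period, and neither 2.1.2.10 nor 4.2 says donation is permitted afterwards. A man who follows 8.6.2 complies with all three. The donation gaps above are therefore differences between clauses, not lost protection.

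**Pregnant partner.** A reader might also infer that she has no cover after treatment. That is too firm. The contraception clause in 2.1.2.10 binds men and their partners without limiting it to partners who can conceive, and it points to 4.2, whose details include condom use with a pregnant woman. One can fairly read 2.1.2.10 as setting the duration and 4.2 the method. The clause also runs for study participation, which outlasts dosing: 6.1 speaks of participation beyond 30 days after the last dose, survival follow-up is every 3 months, and finishing treatment is not an off-study criterion in 3.6.2. Against this, contraception is an odd word for a woman already pregnant, and the one sentence that names her gives the olaparib date. It remains an ambiguity.

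**During treatment.** The 4.2 condom duty still applies while EP0057 is given alone. Only the period after treatment is in doubt.

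None of this explains why the two sentences leave EP0057 out. The reply limits the size of the problem but does not justify the wording.

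**Conclusion.** The wording is wrong for a permitted course of treatment and inconsistent with the rest of the protocol. For donation it is a conflict between 2.1.2.10 and 4.2 on one side and 8.6.2 on the other, with no protection lost if 8.6.2 is followed. For condom use with an already pregnant partner, the only explicit post-treatment period is the olaparib-only one.

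For given n, the tabulated shortfall (17, 45, 73 or 91 days) is an upper bound, reached on the narrow reading of 2.1.2.10; on the broad reading it is zero. These figures rest on an assumed number of EP0057-only cycles. Long courses of EP0057 alone are likely to be uncommon: section 10.1 cites median PFS of 1.5 to 4.3 months with topotecan in relapsed SCLC, although the protocol does not say how often olaparib is stopped first.

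This is a minor internal inconsistency in an operative safety instruction, not a design choice. It has no bearing on the statistical analysis, but it should be corrected because the correction is simple.

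**What to change.** In the donation sentences of 2.1.2.10 and 4.2, write: *while taking either study drug and for 3 months after the last dose of EP0057 or olaparib, whichever is later*.

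In the 4.2 condom sentence, write: *during treatment and for 3 months after the last dose of EP0057 or olaparib, whichever is later*. This also settles the pregnant-partner ambiguity.

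The same donation wording appears in 2.1.1.8, 2.1.3.8 and 2.1.4.11. Phase I is complete and accrual to the urothelial and mCRPC cohorts has closed, so matching edits there are optional, as is adding *whichever is later* to 8.6.2.

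The cost is a short wording change in two sections at the next amendment, with no new procedures and no change to the analysis.
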